### Criteria for Study Continuation and EVL addition (1 to 2 months post-LT):

1. Currently on TAC + prednisone +/- MPA therapy with no contraindication to starting EVL (i.e. wound infection; significant proteinuria (urine prot/cr ratio  $\geq 1.0$ ), hepatic artery thrombosis/stenosis, cytopenias (WBC  $< 1.5$ , ANC  $< 1.0$ , Platelet  $< 30$ , Hemoglobin  $< 7$ ), other deemed by investigator)
2. No more than 2 rejection episodes or 1 steroid-resistant rejection requiring lymphodepletion therapy
3. No active biliary, infectious, or malignant process
4. eGFR  $\geq 30$  ml/min/1.73m^2
5. No significant liver function abnormalities (Direct bilirubin, AST/ALT, Alkphos  $\geq 2x$  elevated)
6. If on current or prior antiviral therapy, HBV and HCV viral load should be undetectable
7. No combined transplantation (e.g. should be primary liver transplant alone)

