## 7 Visit schedule and assessments

**Table 7-1 Assessment schedule**

Visit**	1	2	3	4	5	6	7	At rejection***	Early Term./Study Comp.
Day	-90 to 0 +30 (Tx)	0	30	90	120	135	180		
Inc./Exc. Criteria	X		X	X	X				
Obtain informed consent	X								
Physical Exam			X	X	X		X		
Donor/Recipient Collections		X*							
Blood (Flow, PBMC, RNA, sera)			X*	X	X	X	X	X	
Tissue RNA								X	
Study Completion Form						X	X		X

\*unfunded and not mandatory for this protocol

\*\*  $\pm$  1 month window allowable

Visit 1 = Patient enrollment SOC visit (I/E criteria, informed consent)

Visit 2= Transplant SOC- if possible, donor spleen/lymph nodes and recipient lymph node/blood

Visit 3= Day 30 SOC visit- if Inc./Exc. criteria met, add everolimus and stop MPA if being used. Collect blood if possible (unfunded for this study).

Visit 4= Day 90 SOC visit- if Inc./Exc. criteria met, start tacrolimus withdrawal. Collect blood.

Visit 5= Day 120 SOC visit- if Inc./Exc. criteria met, stop tacrolimus. Collect blood.

Visit 6 = Day 135 visit- collect blood.

Visit 7= Day 180 SOC visit- Study termination. Collect blood.

\*\*\*At any biopsy concerning for rejection: Collect blood and tissue in RNAlater. If rejection, study termination.

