## **7.3 Efficacy**

The major efficacy assessment is the percentage of patients successfully withdrawn from TAC therapy in favor of EVL therapy without rejection or major complications. Rejection will be evaluated by liver biopsy when indicated (typically 2-3 fold increase in liver aminotransferases). If rejection occurs during any point of the trial following EVL addition, the study will be terminated for that patient.

Other efficacy endpoints will be the improvement in TAC side effects (renal, neurologic, metabolic, etc.) and development of EVL side effects (hyperlipidemia, edema, proteinuria, etc) in those successfully withdrawn from TAC without rejection. For those unable to withdraw from TAC due to rejection, we will assess for TAC side effects and EVL side effects if this drug is continued following rejection. Liver and renal function, and hematological parameters will be followed per SOC throughout this biomarker study

The PI and research coordinator will perform these assessments at the study time points at Northwestern and at any intervening time point if the patient needs a liver biopsy to exclude rejection or other complication (hospitalization, infection, etc.). Patients enrolled also will be contacted by phone for any changes in their immunosuppression dosing or other medications in between visits.

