#### **7.4.4 Laboratory evaluations**

At liver transplant donor/recipient collection of lymph nodes and liver biopsy tissue will take place if the patient is consented prior to transplantation. Liver biopsy tissue will also be collected at the time of a suspected rejection.

Blood samples for flow cytometry, PBMCs, RNA and sera will be collected at visits 3, 4, 5, 6, 7 and rejection.

Standard SOC laboratory tests will be performed per our transplant center post-LT protocol: CBC, CMP, trough IS levels three times weekly (0-1 month post-LT), two times weekly (1-3 months post-LT), one time weekly (3-6 months post-LT).

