## **10 Data analysis**

### **10.1 Populations for analysis**

Since there is no randomization in the study, the groups that are analyzed are those that have rejection before TAC-WD, those who develop rejection during/after TAC-WD, and those who never have rejection before or after TAC-WD.

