i) Blood Immunophenotyping. The approach will be to conduct flow cytometry immunophenotyping of peripheral blood before TAC-WD initiation (1 to 2 months and 3 months ( $\pm$  1 month)), right at total TAC-WD (4 months ( $\pm$  1 month)), 2 weeks after full TAC-WD (4.5 months ( $\pm$  1 month)) and study end (6 months ( $\pm$  1 month)) post-LT to analyze cellular changes. Methods: The Immune Monitoring Laboratory at NU (Co-Director [name]) will perform the immunophenotyping. PBMC are isolated from heparinized 30 cc samples on Ficoll-Hypaque gradients. Surface markers are detected with monoclonal antibodies for the T cell subsets CD3, CD4, CD8, CD25, CD45RA, CTLA4 and CD127 followed by fixation/permeabilization/incubation with human FOXP3 antibodies and final flow cytometric analysis. RBC-lysed peripheral blood is also labeled with monoclonal antibodies for T cell subsets, naïve/memory/regulatory B cells (CD19, CD27, IgD, IgM, IL-6), monocytes (CD14) and NK cells (CD56) to quantify the absolute cell numbers per  $\mu$ L. In addition, dendritic cell surface markers are analyzed as follows: monocyteoid vs. plasmacytoid (CD11c; CD123) ratio; antigen processing markers (CD83; CD205); markers inducing Tregs (ILT3; ILT4). For statistical analysis, we perform within subject comparisons on PBMC for both successful and failed TAC-WD/EVL groups using appropriate paired analysis (paired t-test or Wilcoxon Signed Rank test). For the main hypothesis testing, repeated measures of analysis of variance (RM-ANOVA) are used to test the trajectory variations between the groups on PBMC over time. Two-sided F-test statistics are applied;  $\alpha=0.05$  (stats by NU Transplant Statistician).

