### **10.2.3 Handling of missing values/censoring/discontinuations**

In this study, discontinuation will usually be due to rejection occurring during the study protocol (TAC-WD/EVL). While unlikely as this trial is a small pilot study, patients lost to follow-up will be removed from the trial and analysis.

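### The main RM-ANOVA uses a sampling series that ends at month 6, but rejection both defines the failed group and ends its sampling, and no rule covers the visits lost

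*Combined protocol and SAP*

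**What the plan says.** **The test.** Section 10.2, part i, names the main hypothesis test for the immunophenotyping: "repeated measures of analysis of variance (RM-ANOVA) are used to test the trajectory variations between the groups on PBMC over time". The synopsis and Section 10.3.3 repeat it. All three texts list samples at about months 3, 4, 4.5 and 6; Section 10.2 adds one at 1 to 2 months. Table 7-1 marks that early sample (Visit 3) as unfunded and not mandatory.

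**The groups.** Section 10.2.1 defines success as no rejection and failure as rejection.

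**What rejection does to sampling.** Section 7.3: "If rejection occurs during any point of the trial following EVL addition, the study will be terminated for that patient". Table 7-1: "At any biopsy concerning for rejection: Collect blood and tissue in RNAlater. If rejection, study termination". Section 7.4.4: "Blood samples for flow cytometry, PBMCs, RNA and sera will be collected at visits 3, 4, 5, 6, 7 and rejection". No draw is scheduled after a rejection. The month-6 visit is itself the end of the study: "Visit 7= Day 180 SOC visit- Study termination. Collect blood".

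**Missing data.** Section 10.2.3 says "discontinuation will usually be due to rejection occurring during the study protocol". The only rule that follows removes patients lost to follow-up. Section 10.2.4 lists no supportive analyses.

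**Expected numbers and timing.** Section 10.4 expects 20 patients to enter withdrawal, 4-5 with rejection and 14-15 without. Section 3 expects rejection in 20%, one to two months after withdrawal.

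**The concern.** The event that assigns a patient to the failed group also removes that patient's later samples. A patient who reaches Visit 7 without rejection is a success when the study closes, and a patient who rejects earlier never has Visit 7. The possible exception is a Visit 7 draw at or just before a rejection biopsy, and the plan does not say how that patient is classified.

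On its natural reading, then, the named test compares two groups over a series whose last point exists in essentially one of them. Analysts following the same text could find that no test can be computed, or could drop month 6 on their own authority. Section 3.3 makes the next study depend on whether the primary endpoint is met, so the time points and the handling of lost visits should be settled before the data are seen. Section 10.2 also aims to predict rejection before it happens, which requires pre-rejection samples.

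**Working it through.** **1. The plan's own numbers.** 25 enrolled × 0.80 = 20 entering withdrawal. A 20% rejection rate gives 20 × 0.20 = 4 failures and 16 successes. The 15 and 5 in Figure 6 correspond to 25%. Section 10.4's 4-5 and 14-15 are close to both. Below I use 4 or 5 failures and 15 successes.

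**2. Degrees of freedom for group-by-time.** Count the group-by-visit cells that contain data. Subtract the parameters for intercept, group (where both groups are present) and time.
- Visits 4-7 as planned: 8 cells − (1 + 1 + 3) = 3.
- All pre-rejection data, with the failed group's month-6 cell empty: 7 − (1 + 1 + 3) = 2. The month-6 group contrast is not estimable.
- Complete rows only, with no failures left: 4 − (1 + 3) = 0. There is no between-group test.
- With Visit 3 added: 9 − (1 + 1 + 4) = 3, against 10 − 6 = 4 as planned.

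**3. How much of Visit 6 is also lost.** Day 0 is the day tacrolimus stops. The share of failures with a pre-rejection Visit 6 sample is the part of the rejection interval that falls after Visit 6, assuming rejections are spread evenly over it. The continuation criteria set 14 days as the minimum gap between Visits 5 and 6. If tacrolimus stops on day 120, the latest Visit 6 (day 135 + 30 = 165) is 45 days later.

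| Rejection interval | Visit 6 at day 14 | day 30 | day 45 |
|---|---|---|---|
| Days 30-60 (Section 3 timing) | 30/30 = 100% | 30/30 = 100% | 15/30 = 50% |
| Days 0-60 (assumed) | 46/60 = 77% | 30/60 = 50% | 15/60 = 25% |
| Days −30 to 60, from start of taper (assumed) | 46/90 = 51% | 30/90 = 33% | 15/90 = 17% |

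The 45-day gap is not the extreme. If Visit 5 is at day 90 and Visit 6 at day 165, the gap is 75 days. On the Section 3 timing, no failure would then have a pre-rejection Visit 6 sample.

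**4. Precision.** 95% CI half-width for the between-group difference in change, in SD of change: t(0.975, n1 + n2 − 2) × √(1/n1 + 1/n2), with n1 = 15 successes.
- 5 failures: 2.101 × 0.516 = 1.08
- 4 failures: 2.110 × 0.563 = 1.19
- 3 failures: 2.120 × 0.632 = 1.34
- 2 failures: 2.131 × 0.753 = 1.60

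**5. Why the at-rejection sample should not fill the gap.** This was simulated with a within-patient correlation of 0.5 and no group difference before rejection (both assumed). Putting the at-rejection sample in the last slot, a 1 SD shift at rejection alone gave p < 0.05 in 40% of trials (4 vs 16) and 47% (5 vs 15). The same test on three pre-rejection visits stayed near 5%. Such a result would show that rejection was present, not that it had been predicted.

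**The case against.** **Month 6 in the test is an inference.** The RM-ANOVA sentence says only that it runs over time, and Section 10.2.1 defines the variable as before and during withdrawal. This stands as a caution. However, all three statements of the test follow a list ending at month 6, none restricts it, and Section 10.2 also speaks of markers after withdrawal.

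**It is an unpowered pilot, and a test with 0 df would be noticed.** True. But noticing it leads to an unplanned choice after the data are in. The point asks for a computable test, not for power.

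**Withdrawn patients are still followed.** Section 6.3.7 provides this only under standard care, with no research blood. The early-termination column of Table 7-1 carries only a completion form.

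A reader might also infer three stronger points that the documents do not support:
- *The RM-ANOVA mixes in blood drawn at rejection.* All three texts specifying the test omit that sample. What stands is a separate conflict: Section 4 says it is assayed, while Section 3.3 and Figure 6 treat it as stored.
- *Three groups enter the test, and the early-rejection group supplies complete rows.* Section 10.1 does list "those that have rejection before TAC-WD, those who develop rejection during/after TAC-WD, and those who never have rejection before or after TAC-WD", but the primary comparison is stated as successful against failed withdrawal in the synopsis and Sections 3.1, 10.2 and 10.2.1. Whether early rejectors reach withdrawal is itself unclear. Section 5.2 continues patients with "No more than 2 rejection episodes or 1 steroid-resistant rejection requiring lymphodepletion therapy" and reuses that criterion at month 3, whereas Section 5 names absence of rejection among the month-3 checks.
- *Only one or two failures would have a Visit 6 sample.* That needs an assumed even spread of rejection from the start of the taper. On the Section 3 timing, Visit 6 is intact at day 14 or 30.

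**Conclusion.** The concern holds. On the natural reading, the main between-group test cannot use its last time point: few if any failures can have a month-6 sample, and Section 10.2.3 has no rule for visits lost to rejection. Group-by-time df over Visits 4-7 falls from 3 to 2 with all pre-rejection data, and to 0 if only complete rows are kept and no failures remain.

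On the protocol's expected timing the loss is mainly month 6, with Visit 6 affected if it falls late in its window. Larger Visit 6 losses rest on assumed earlier rejection. The half-widths of 1.08 to 1.19 SD assume that every expected failure contributes and that both groups have the same SD of change. They show that even the repaired test is imprecise, so the estimate and interval matter more than the p-value. This should be fixed before analysis.

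**What to change.** 1. **Synopsis and Sections 10.2 and 10.3.3.** Make the between-group test successful against failed withdrawal, on samples drawn before rejection at Visits 4, 5 and 6. Use a linear mixed model with small-sample degrees of freedom that keeps patients with incomplete visits. State its assumption that lost visits are missing at random given group and earlier values. Use the optional Visit 3 sample only in a supportive analysis, so that the main test does not depend on an unfunded draw.
2. **Section 10.2.3.** State that visits after rejection are missing and are not replaced by the at-rejection sample. State how a rejection biopsied at or just after Visit 7 is classified. Report the number of failures contributing at each visit, and the between-group difference in change with a 95% CI.
3. **Month 6.** Show it in successes only, descriptively or with the paired tests already planned.
4. **Reconcile the texts.** Section 4 must agree with Section 3.3 and Figure 6 on whether the at-rejection sample is assayed or stored. Section 5 must agree with the continuation criteria in Section 5.2 on whether patients with earlier rejection enter withdrawal. In the analysis, classify any who do enter by their withdrawal outcome, with a sensitivity analysis excluding them.

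**Cost.** Wording only, with no new samples or visits. The downside is that month 6 leaves the between-group test, so later changes after withdrawal are described in successes only.

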Equally important as the chosen IS regimen is identifying predictive biomarkers, such as those we have tested above. Various reports demonstrate a higher percentage of CD4+CD25highFOXP3+ cells, DC2,  $\gamma\delta$  T cells and specific genomic signatures in tolerant LT recipients versus those on maintenance IS. Our collaborative group has previously performed proteogenomic assays (mRNA profiles, proteomic analytes) to identify markers of acute rejection (AR) and chronic allograft nephropathy in kidney recipients, as well as CKD post-LT. In addition, we recently conducted a study profiling (mRNA gene expression) 114 blood and 57 liver biopsy samples of patients with different clinical phenotypes, and have identified both blood and tissue mRNA signatures that can distinguish AR from other major causes of graft injury (hepatitis C recurrence, mixed HCV-R and AR, other causes) in LT recipients with high predictive accuracy (AUC 0.89 – 0.9; Figure 5). These biomarkers have the potential to be useful to enhance the specificity of diagnosis, particularly in managing patients with contrasting etiologies (e.g., AR vs. HCV-R). In addition, the immune/inflammatory nature of these AR profiles may help inform decisions to perform liver biopsies and in immune monitoring during immunosuppression reduction, as proposed herein. Yet, the presence of ‘snap-shot’ non-specific cell populations and differential gene/protein arrays only provides circumstantial evidence for their role in immunoregulation. Prospective sequential assays would provide a more accurate measure of the effects of mTOR-I on immunoregulation. We anticipate that these expression patterns will be useful as regulatory signatures that may predict successful CNI withdrawal, as suggested by our recent trial and other reports.

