3) Finally, in either scenario, there may be interest from our group or Novartis in comparing diagnostic (not predictive) peripheral blood and biopsy genomic biomarkers at the time of AR occurring before and after TAC WD/EVL. We have already identified genomic AR signatures in blood and biopsy from our prior work (all TAC-treated recipients), which can serve as comparative data for this trial. There may be differences in AR signals in TAC-treated patients vs. those who have TAC withdrawn and are on EVL monotherapy. With additional future funding, we can perform the same mRNA as above at the time of any AR and compare rejections that occur pre- and post-TAC withdrawal. This will help identify signals that may be more specific of EVL (CNI-free) rejection to be able to clinically utilize these signals to guide diagnosis and patient management. Also, we can determine if biopsy vs. peripheral blood biomarker AR signals are similar or different, so as to ascertain if blood instead of biopsies (which are risky & costly) can be utilized for rejection diagnosis specific to EVL (CNI-free) therapy. For now, we will store blood (sera/plasma, PBMC, RNA) and biopsy tissue (RNAlater) at the time of AR if these analyses are of future interest.

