ii) Gene Expression Microarrays: The approach will be to conduct parallel serial genomic bioassays of peripheral blood before and after attempted TAC-WD/EVL (same time points as immunophenotyping). Methods: The Genomics Core at Scripps Clinic (Director, [name]) will perform the microarray analysis. Blood will be collected in PaxGene tubes and sent to Scripps for the gene microarrays. Affymetrix® Hu133 Plus Peg microarrays will be used to test for differentially expressed genes between those developing AR vs. without AR during TAC WD. We will also perform biological function and canonical pathway mapping of several immune/inflammatory gene pathways. For statistical analysis, we report for each mRNA and microRNA comparison the T-test p-value, its non-parametric analog (Kruskal Wallis test), the fold change, and for multi-analyte signatures, the area under the receiver operating curve (concordance index/C-index) and q-values by member genes/proteins. We then calculate the predictive accuracy, sensitivity and specificity of each signature (statistics by [name] informatics group at Scripps Clinic)

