### **10.2.1 Variable**

The main variables are the peripheral blood Treg% (or other immunoregulatory cells) and mRNA AR signatures seen prior to and during either successful (no rejection) vs. failed (rejection) TAC-WD/EVL.

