## 10.4 Sample size calculation

As this is an exploratory pilot study, we will enroll an initial 25 patients, 20 of who are expect to undergo TAC-WD/EVL. Of these, we expect 14-15 will not have AR during TAC-WD and 4-5 are expected to have AR, based on the initial EVL clinical trial. This will allow us to have preliminary information to proceed ahead to one of a few different directions, as outlined in Exploratory Objectives. Therefore, a power analysis was not needed for this pilot study.

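### The primary genomic variable is an AR signature that the plan does not identify, fix in advance or tie to a visit, and 4-5 v 14-16 patients are too few to both choose and evaluate one.

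*Combined protocol and SAP*

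**What the plan says.** Sections 3.1 and 10.2.1 name the primary genomic variable; in 10.2.1 it is "mRNA AR signatures seen prior to and during either successful (no rejection) vs. failed (rejection) TAC-WD/EVL". Section 10.2.2 adds no method and refers back to Section 10.2.

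Section 10.2 ii), repeated in Section 10.3.3 and in shorter form in the synopsis, has two layers:

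- Gene level: "we report for each mRNA and microRNA comparison the T-test p-value, its non-parametric analog (Kruskal Wallis test), the fold change".
- Signature level: "for multi-analyte signatures, the area under the receiver operating curve (concordance index/C-index) and q-values by member genes/proteins", followed by "We then calculate the predictive accuracy, sensitivity and specificity of each signature".

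None of these sections lists the signatures, says whether they are set before the data are seen, names a decisive visit, gives a q cut-off or describes cross-validation.

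Section 1 reports that the group, from 114 blood and 57 biopsy samples, "have identified both blood and tissue mRNA signatures that can distinguish AR from other major causes of graft injury", with AUC 0.89-0.9. Section 3.3 item 3 returns to this: "We have already identified genomic AR signatures in blood and biopsy from our prior work (all TAC-treated recipients". There the signatures are comparative data for a diagnostic comparison at the time of rejection, dependent on future funding. No other analytic use is stated.

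On size, Section 10.4 says "we will enroll an initial 25 patients, 20 of who are expect to undergo TAC-WD/EVL" and "we expect 14-15 will not have AR during TAC-WD and 4-5 are expected to have AR". The Figure 6 footnote gives 15 v 5. Section 3 expects 20% rejection.

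**The concern.** Section 3.3 makes the next step depend on whether the primary endpoint is met. If it is, the group seeks funding for a larger trial of these biomarkers; if not, it moves to other assays on the stored samples. The genomic half of that decision rests on a signature the plan leaves open. If it is built from the trial's own arrays, the group sizes allow almost any signature to look good. If it is the existing one, the plan should say so, because a fixed score is the one genomic analysis here whose result could be read at face value.

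**Working it through.** **Inputs from the documents.** 20 patients entering withdrawal; 4-5 v 14-15 (Section 10.4); 5 v 15 (Figure 6 footnote); 20%/80% (Section 3); AUC 0.89-0.9 for the existing signature (Section 1).

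**Assumed, because the documents give no figure.** 20,000-55,000 probe sets (m); q<=0.05; p<0.0001 as an illustrative gene-level threshold; equal-variance binormal scores.

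**1. The plan's own split.** 20 x 0.20 = 4 and 20 x 0.80 = 16. With Section 10.4 and Figure 6, non-rejecters number 14, 15 or 16. The splits 4 v 14, 4 v 16 and 5 v 15 span the range for the results below.

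**2. Smallest p a rank test can give.** At perfect separation the exact two-sided p is 2/C(N, n1). The Kruskal-Wallis statistic is H = 3 n1 n2/(N+1), referred to chi-square on 1 df. By Benjamini-Hochberg, the number of genes that must all sit at that floor for q<=0.05 is k = p x m/0.05, rounded up.

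| Split | Exact floor | H | Kruskal-Wallis floor | k, exact (m = 20,000 / 55,000) | k, Kruskal-Wallis |
|---|---|---|---|---|---|
| 4 v 14 | 2/3,060 = 0.00065 | 168/19 = 8.84 | 0.0029 | 262 / 719 | 1,178 / 3,238 |
| 4 v 16 | 2/4,845 = 0.00041 | 192/21 = 9.14 | 0.0025 | 166 / 455 | 999 / 2,747 |
| 5 v 15 | 2/15,504 = 0.00013 | 225/21 = 10.71 | 0.0011 | 52 / 142 | 426 / 1,170 |

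A lone gene therefore cannot pass by rank test, however well it separates the groups.

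**3. The t-test.** It has no floor. For a gene with AUC 0.89, d = sqrt(2) x z(0.89) = 1.73. The noncentrality is d x sqrt(n1 n2/N), for example 1.735 x sqrt(64/20) = 3.10 at 4 v 16. Power at p<0.0001 is 7% (4 v 14), 8% (4 v 16) and 12% (5 v 15).

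Simulated Benjamini-Hochberg at q = 0.05 on 20,000 independent genes shows how yield depends on the truth:

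| True genes, effect | Share found, 4 v 16 | Share found, 5 v 15 |
|---|---|---|
| 200, d = 1.5 | 0.6% | 1.3% |
| 200, d = 2 | 14% | 24% |
| 200, d = 3 | 81% | 91% |
| 1,000, d = 2 | 42% | 56% |

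**4. Choosing and evaluating on the same patients.** With 20,000 independent null genes, I took the 20 with the smallest t-test p, summed them with their signs and computed the AUC in the same patients. It was 1.0 in all 50 runs at each of the three splits.

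**5. One locked score, one visit, two-sided 0.05.** Same d and noncentrality, no multiplicity.

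| True AUC | 4 v 14 | 4 v 16 | 5 v 15 |
|---|---|---|---|
| 0.89 | 82% | 84% | 89% |
| 0.75 | 35% | 37% | 42% |
| 0.70 | 23% | 24% | 27% |

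By the Hanley-McNeil standard error, an observed AUC of 0.89 has a 95% CI of about 0.67-1.00 (4 v 16) or 0.69-1.00 (5 v 15). Testing two visits at 0.025 each lowers power per visit to 74-81% at AUC 0.89 and 26-30% at 0.75 (4 v 16 and 5 v 15).

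**The case against.** Several stronger readings are tempting, and the documents do not support them.

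- **That the analysis is only gene by gene, so the primary variable is never tested.** The sentence with the gene-level tests goes on to plan signature AUCs, and the next adds accuracy, sensitivity and specificity. Signature-level evaluation is planned; what is missing is the identity of the signatures.
- **That the existing AR signature is excluded.** This would be an inference from silence. The variable as worded could include it, the Section 10.2 rationale rests on AR being diagnosable in blood by microarray, and Section 10.3.3 cites the earlier study in its array methods. The documents support only that scoring it is not stated.
- **That q-values will be computed after genes are selected.** The plan ties them to member genes but describes no such order.
- **That the screen must return nothing or chance genes.** Step 3 shows that very large or widespread effects could pass by t-test, and the rank-test floor does not bind the t-test reported beside it.

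Two further objections carry weight. The aim is discovery of immunoregulation metrics in a pilot that claims no power, so a gene search is legitimate and a rejection score should not replace it. And the AUC of 0.89-0.9 was for telling AR from other graft injury, in TAC-treated recipients. Here the score would have to predict later rejection in non-viremic patients selected for reasonably stable liver function. Nothing in the documents shows that 0.89 carries over. The contrast between 7-12% and 82-89% power also largely reflects the different thresholds.

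What stands after this is the undefined signature. Being a pilot does not remove it, because Section 3.3 hangs a funding decision on the result.

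**Conclusion.** The concern holds as a gap in specification that should be closed; it does not invalidate the study. The plan names AR signatures as the primary genomic variable without saying which, fixed when, or read at which visit. At 4-5 v 14-16 patients the gene screen cannot make up for this. A lone gene cannot reach q<=0.05 by rank test, one strong gene has 7-12% t-test power at p<0.0001, and a signature both chosen and evaluated on these patients can look perfect under the null.

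The rank-test result rests on the assumed probe count and q cut-off, the t-test figure on the assumed threshold, and the null AUC of 1.0 on independent genes and the simple selection rule in step 4. The locked-score power depends almost wholly on transfer: good at AUC 0.89, poor at 0.75 or below. It also assumes 4-5 rejections; at a true rate of 20%, the chance of 2 or fewer among 20 is 21%. Even at low power, a locked score gives an AUC and interval free of selection bias.

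**What to change.** In Section 10.2 ii), and likewise in the synopsis and Section 10.3.3:

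1. Add one prespecified confirmatory genomic analysis: a single score per array from the existing blood AR signature, with genes and weights frozen before the arrays are linked to outcome.
2. Compare rejecters with non-rejecters, among patients who start withdrawal, at one named pre-rejection visit. Visit 4 is an example: it comes before withdrawal starts, so no rejection during or after withdrawal has yet removed a patient. Make Visit 5 supportive, or split alpha. Report AUC with 95% CI.
3. Keep the gene and immunoregulation search as discovery, with q-values over all probe sets before any selection.
4. Report accuracy beside what is obtained by calling every patient a success: 15/20 = 75% to 16/20 = 80%.
5. Reconcile the expected splits in Sections 3 and 10.4 and Figure 6.

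The cost is SAP wording and a small scoring step on arrays already planned, with no new patients or samples. The downside is that the signature is diagnostic and came from TAC-treated patients. It may transfer poorly, and a negative result would not rule out other signatures. Whether the score becomes the sole primary analysis, and whether Kruskal-Wallis p-values stay, are matters of choice.
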